9.9. Other Safety Measures

No additional safety measures are planned.

10. PHARMACOKINETICS

10.1. Graphical and Tabular Summaries of Pharmacokinetic Profiles

The PK Analysis Subset will be used when summarizing plasma and urine PK concentrations. For both measured analytes in each specimen type, concentrations below the limit of quantification (BQL) collected before the first measurable PK concentration above the lower limit of quantification (LLOQ) will be treated as 0 for plotting and for all calculations including noncompartmental analysis (NCA) and concentration summary statistics. All other BQL values, for each analyte within each specimen type, observed after the first measurable concentration will be treated as missing. There will be no imputation of missing concentrations. The geometric mean (GM) of concentrations will be treated as missing for sets of data points containing a BQL value.

Collection of plasma or urine samples outside of the protocol defined time window for the timepoint will not result in exclusion of the sample result from NCA. Plasma or urine samples collected out of window will be evaluated on a case by case basis. Results from PK plasma samples that were collected substantially outside of the protocol defined time window will be excluded from concentration summary statistics by nominal timepoints and plots of mean concentration by nominal timepoint. Substantially out-of-window samples are defined to be twice the size of the protocol required windows: \pm 10 minutes of the nominal timepoint for the 0.5 h post dose sample; \pm 20 minutes of the nominal timepoint for the remaining post dose samples on Day 1; \pm 1 hour of the nominal timepoint for the remaining inpatient days, Day 2, Day 3, and Day 4; \pm 2 days for the follow-up visits, Day 7 and Day 14; and \pm 4 days for the final study visit, Day 21.

If the exact time of plasma PK sample collection is not recorded then the collection time will be imputed as the planned time for analysis, as long as it is not known that the sample was collected outside of the protocol defined window. If the start and/or end time of a urine PK sample is unknown then the missing time(s) will be assumed to be the planned sample collection time (start or end), as long as it is not known that the sample was collected outside of the protocol defined window. If the exact collection time is not known for either sample type, but it is known that the sample was collected outside of the protocol defined time window, then the timepoint may be excluded from analysis at the discretion of the PK analyst. Rationale for excluding results from analysis will be described in the CSR. Results from samples with imputed collection times will be indicated in listings of PK sample concentrations.

All subjects who have at least one quantifiable concentration of VT-1598 or VT-11134 measured will be included in the PK Analysis Population. The bioanalytical laboratory will report VT-1598 and VT-11134 concentrations in plasma and urine in units of ng/mL. Concentrations in plasma and urine will be reported in the same units in the CSR, while cumulative amounts excreted into urine will be reported in units of mg. Drug and metabolite concentrations in plasma and urine will be summarized by Dose Group and listed by subject:

- Subject level concentrations of VT-1598 and VT-11134 in plasma ([Listing 30](#)) and in urine ([Listing 31](#)).
- Subject specific plasma PK parameters for VT-1598 ([Listing 32](#)) and for VT-11134 ([Listing 33](#)).
- Subject specific urine inpatient PK parameters ([Listing 34](#)) and urine nominal collection time interval PK parameters ([Listing 35](#)) for VT-1598 and for VT-11134 ([Listing 36](#) and [Listing 37](#)).

Subject level PK concentration listings will include separate columns for concentrations reported by the lab and concentrations used for analysis. The lab reported concentrations may include codes, such as: "BQL" or "QNS" (Quantity not Sufficient), while the analysis concentrations will contain numeric data only, including imputed values such as 0 for pre-dose timepoints and BQL samples prior to the first quantifiable sample.

Listings will also indicate the nominal time (i.e., the planned time) and actual post dose time in hours associated with the sample and will note sample times which were collected out of window, substantially out of window, or imputed.

Individual and PK concentrations will be presented in tables and figures by Dose Group and nominal timepoint:

- The GM and coefficient of variation (CV) of individual concentrations in plasma will be presented tabularly by Dose Groups for both VT-1598 ([Table 45](#) for sampling times between 0 and 14 hours post dose and [Table 46](#) for sampling times between 24 and 480 h post dose) and VT-11134 ([Table 57](#) for sampling times between 0 and 14 hours post dose and [Table 60](#) for sampling times between 24 and 480 hours post dose).
- Individual concentrations in plasma and summary statistics will be presented tabularly for each Dose Group for VT-1598 (beginning at [Table 47](#) and continuing through [Table 58](#)) and for VT-11134 (beginning at [Table 59](#) and continuing through [Table 72](#)).
- Individual concentrations in plasma will be presented graphically during the inpatient sampling time period (0 h, 0.5 h, 1 h, 1.5 h, 2 h, 3, h, 4 h, 6 h, 8 h, 10 h, 12 h, 14 h, 24 h, 36 h, 48 h, 60 h, 72 h post dose). For VT-1598, the 40 mg, 80 mg, 320 mg, and 640 mg Dose Groups will be presented in [Figure 65](#) and the 160 mg fasted and 160 mg fed Dose Groups will be presented in [Figure 66](#). For VT-11134, the 40 mg, 80 mg, 320 mg, and 640 mg Dose Groups will be presented in [Figure 69](#) and the 160 mg Fasted and 160 mg Fed Dose Groups will be presented in [Figure 70](#).
- Individual concentrations in plasma will be presented graphically over all sampling timepoints. For VT-1598, the 40 mg, 80 mg, 320 mg, and 640 mg Fasted Dose Groups will be presented in [Figure 67](#) and the 160 mg Fasted and Fed Dose Groups will be presented in [Figure 68](#). For VT-11134, the 40 mg, 80 mg, 320 mg, and 640 mg Fasted Dose Groups will be presented in [Figure 71](#) and the 160 mg Fasted and Fed Dose Groups will be presented in [Figure 72](#).
- Semi-log individual concentration profiles in plasma will be presented graphically during the inpatient sampling time period. For VT-1598 the 40 mg, 80 mg, 320 mg, and 640 mg Fasted Dose Groups will be presented in [Figure 77](#) and the 160 mg Fasted and Fed Dose Groups will be presented in [Figure 78](#). For VT-11134 the 40 mg, 80 mg, 320 mg, and 640 mg Fasted Dose Groups will be presented in [Figure 81](#) and the 160 mg Fasted and Fed Dose Groups will be presented in [Figure 82](#).
- Semi-log individual concentration profiles in plasma will be presented graphically over all sampling timepoints. For VT-1598 the 40 mg, 80 mg, 320 mg, and 640 mg Fasted Dose Groups will be presented in [Figure 79](#) and the 160 mg Fasted and Fed Dose Groups will be presented in [Figure 80](#). For VT-11134 the 40 mg, 80 mg, 320 mg, and 640 mg Fasted Dose Groups will be presented in [Figure 83](#) and the 160 mg Fasted and Fed Dose Groups will be presented in [Figure 84](#). Individual cumulative amounts excreted into urine and will be presented graphically for VT-1598 (40 mg, 80 mg, 320 mg, and 640 mg Fasted Dose Groups in [Figure 73](#) and 160 mg Fasted and Fed Dose Groups in [Figure 74](#)) and VT-11134 ([Figure 75](#) and [Figure 76](#)).
- Graphically, plots of mean concentration in plasma profiles will be presented with error bars representing ± 1 SD around each sample timepoint for both VT-1598 ([Figure 85](#) for 0 h to 72 h post dose and [Figure 86](#) for all post dose timepoints) and VT-11134 ([Figure 87](#) for 0 h to 72 h post dose and [Figure 88](#) for all post dose timepoints) by Dose Group.

- Semi-log mean plots will be presented for VT-1598 ([Figure 91](#) for 0 hours to 72 hours post dose and [Figure 92](#) for all post dose timepoints) and for VT-11134 ([Figure 93](#) for 0 hours to 72 hours post dose and [Figure 94](#) for all post dose timepoints) by Dose Group.
- Mean cumulative amount excreted into urine will be presented graphically by Dose Group in plots with error bars representing ± 1 SD around each sample collection time for both VT-1598 ([Figure 89](#)) and VT-11134 ([Figure 90](#)).
- Mean concentration in plasma profiles by analyte will be presented graphically for each Dose Group separately in [Figure 95](#) for the 40 mg and 80 mg Fasted Dose Groups, in [Figure 96](#) for the 160 mg Fasted and Fed Dose Groups, and in [Figure 97](#) for the 320 mg and 640 mg Fasted Dose Groups.
- Mean of cumulative amounts excreted into urine by analyte will be presented graphically for each Dose Group separately in [Figure 98](#) for the 40 mg and 80 mg Fasted Dose Groups, in [Figure 99](#) for the 160 mg Fasted and Fed Dose Groups, and in [Figure 100](#) for the 320 mg and 640 mg Fasted Dose Groups.

10.2. Noncompartmental Analysis

PK parameters from plasma PK data will be estimated through NCA using version 8.2 or higher of Phoenix WinNonlin®. Actual post dose time will be used for the estimation of plasma PK parameters instead of nominal time. In the case of imputed sample collection times, the imputed time will be included in NCA. PK parameters derived from urine concentration data will be calculated using a combination of Phoenix WinNonlin and SAS version 9.4 or above. Any outliers identified in the PK analysis will be discussed in the analysis report. Outliers will not be excluded from the PK analysis.

Summary statistics of PK parameter estimates by Dose Group will be presented in tables. Summary statistics will include the mean, SD, min, max, CV and GM:

- Plasma PK parameters will be summarized and presented tabularly for all Dose Groups for VT-1598 ([Table 73](#)) and VT-11134 ([Table 80](#)).
- Detailed summary statistics of each plasma PK parameter will be presented tabularly for each Dose Group for VT-1598 (beginning at [Table 74](#) and continuing through [Table 79](#)) and VT-11134 (beginning at [Table 81](#) and continuing through [Table 86](#)).
- Urine PK parameters will be summarized and presented tabularly for all Dose Groups for VT-1598 ([Table 87](#)) and VT-11134 ([Table 94](#)).
- Detailed summary statistics of each urine PK parameter will be presented tabularly for each Dose Group for VT-1598 (beginning at [Table 88](#) and continuing through [Table 93](#)) and VT-11134 (beginning at [Table 95](#) and continuing through [Table 100](#)).

The definition of CV is described below:

For an independent identically distributed random sample $\{x_1, x_2, \dots, x_n\}$ from a log-normal distribution, let s^2 be the sample variance statistic of the natural log-transformed values of the sample. The CV will be defined as:

$$CV = \sqrt{\exp(s^2) - 1}$$

Phoenix WinNonlin NCA will use the following settings to compute parameters from plasma PK data:

- Linear Up Log Down calculation method

- Uniform weighting
- Oral dosing
- Lambda Z Acceptance Criteria
 - $Rsq_{adjusted} \geq 0.90$
 - $Span \geq 3$ half-lives
 - Includes at least 3 timepoints after T_{max}

If an insufficient number of subjects meet the Lambda Z Acceptance Criteria for computing plasma PK parameters, then relaxed Lambda Z Acceptance Criteria may be used and will be described in the CSR.

C_{max}

C_{max} is defined as the maximum drug or metabolite concentration observed in plasma over all PK sample concentrations. It will be obtained from the **C_{max}** parameter calculated by WinNonlin. If there is no measurable concentration in the subject's PK profile, then **C_{max}** will be missing for that subject. **C_{max}** will be reported in units of ng/mL.

T_{max}

Time of maximum concentration (**T_{max}**) is defined as the time at which the **C_{max}** occurs. It will be obtained from the **T_{max}** parameter calculated by WinNonlin. If there is no measurable **C_{max}** in the subject's PK profile, then **T_{max}** will be missing for that subject. **T_{max}** will be reported in units of h.

λ_z

The terminal phase elimination rate constant (**λ_z**) is defined as the first-order rate constant describing the rate of decrease of drug or metabolite concentration in the terminal phase (defined as the terminal region of the PK curve where drug or metabolite concentration follows first-order elimination kinetics). **λ_z** will be computed as the slope of a terminal region consisting of ≥ 3 successive points in the plot of log-transformed concentration data versus time. **λ_z** will be estimated using uniform weighting.

Timepoints used in the estimation of **λ_z** will be initially selected using the WinNonlin automatic algorithm. Manually chosen timepoints may be used at the discretion of the PK analyst after examination of the automatically chosen points in the context of the semi-log profile to improve estimation of **λ_z** on a case-by-case basis. The set of points chosen must contain only timepoints after **T_{max}**, include at least 3 timepoints, and satisfy the Lambda Z Acceptance Criteria described above. Otherwise, the elimination rate constant and all derived parameters (apparent terminal elimination half-life [$t_{1/2}$], AUC Extrapolated to Infinity [$AUC_{0-\infty}$], apparent Clearance [CL/F], and apparent volume of distribution during terminal phase [V_d/F]) will be treated as missing.

This parameter will be obtained from the **Lambda_z** parameter calculated by WinNonlin. **λ_z** will be reported in units of 1/h.

t_{1/2}

The **t_{1/2}** is defined as the time required for the drug or metabolite concentration to decrease by a factor of one-half in the terminal phase. The **t_{1/2}** can be estimated as $\ln(2)/\lambda z$. It will be obtained from the **HL_Lambda_z** parameter calculated by WinNonlin. Half-life will be reported in units of h.

AUC

$AUC_{0-\text{last}}$ is defined as the area under the concentration-time curve from dosing (time 0) to the time of the last measured concentration. $AUC_{0-\text{last}}$ will be estimated using the Linear Up Log Down calculation method and obtained from the **AUClast** parameter calculated by WinNonlin.

$AUC_{0-\text{inf}}$ is defined as the total area under the concentration-time curve from dosing (time 0) taken to the limit as the end time becomes arbitrarily large. $AUC_{0-\text{inf}}$ can be calculated by adding $AUC_{0-\text{last}}$ to an extrapolated value equal to the last measured concentration greater than the LLOQ divided by λz :

$$AUC_{0-\text{inf}} = AUC_{0-\text{last}} + \frac{C_{\text{last}}}{\lambda z}$$

Where C_{last} is the last measured concentration \geq LLOQ. $AUC_{0-\text{inf}}$ will be obtained from the **AUCINF_obs** parameter calculated by WinNonlin®.

% AUC_{ex} is defined as percentage of $AUC_{0-\text{inf}}$ obtained by extrapolation from time of the last measured concentration to infinity. % AUC_{ex} can be calculated by dividing AUC from time of the last measured concentration to infinity by $AUC_{0-\text{inf}}$:

$$\%AUC_{\text{ex}} = \frac{AUC_{0-\text{inf}} - AUC_{0-\text{last}}}{AUC_{0-\text{inf}}},$$

If % AUC_{ex} is $>20\%$, the estimated $AUC_{0-\text{inf}}$ will be excluded from statistical summaries of PK parameter estimates and downstream calculations. % AUC_{ex} will be obtained from the **AUC_%Extrap_obs** parameter calculated by WinNonlin.

All AUCs will be reported in units of ng*h/mL.

CL/F

Apparent oral clearance (CL/F) will be obtained from Dose/ AUC_{inf} . If % AUC_{ex} is $>20\%$, the estimated CL/F value will be excluded from statistical summaries of parameter estimates and downstream calculations. CL/F will be obtained from the **CL_F_obs** parameter calculated by WinNonlin. Clearance will be reported in units of L/h.

V_d/F

Apparent volume of distribution (V_d/F) will be calculated as $(CL/F)/\lambda z$. If % AUC_{ex} is $>20\%$, the estimated V_d/F value will be excluded from statistical summaries of parameter estimates and downstream calculations. V_d/F will be obtained from **Vz_F_obs** calculated by WinNonlin. Volume will be reported in units of L.

Ae_{last}

Ae_{last} is defined as the cumulative amount of drug or metabolite excreted into urine up to the collection time of the last measurable concentration. Amount of drug or metabolite will be reported in units of mg.

$Ae\%_{\text{Dose}}$

$Ae\%_{\text{Dose}}$ is defined as the percent of drug (VT-1598) excreted into urine up to the ending time of the last measurable concentration. $Ae\%_{\text{Dose}}$ will be obtained from $Ae_{\text{last}}/\text{Dose} * 100\%$.

CL_R

CL_R is defined as the renal clearance of drug or metabolite and will be calculated as Ae_{last}/AUC_{0-t1}. Where AUC_{0-t1} is defined as AUC from dosing (time 0) to collection time (t1) based on the last collected concentration in urine (0 h to 72 h post dose). AUC_{0-t1} will be converted to mg*min/mL for calculations of CL_R. CL_R will be treated a missing if AUC_{0-t1} or Ae_{last} is not estimable. Renal clearance of VT-1598 or VT-11134 will be reported in units of mL/min.

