## Nonclinical Drug Metabolism and Pharmacokinetics

### Pharmacokinetics

Single-dose PK studies were conducted in Swiss albino mice, Sprague-Dawley rats, Beagle dogs, and cynomolgus monkeys, with the primary goal to identify the version/form and formulation that would give optimized exposures for preclinical safety assessment. Repeat-dose PK and toxicokinetics studies showed that orally administered VT-1598 was well absorbed and reached a maximum measured plasma concentration ( $C_{max}$ ) of 30-40 µg/mL in rats and 50-60 µg/mL in monkeys after repeated doses up to 28 days in duration. VT-1598 exposures increased as doses increased in all animal species, but exposure increases were less than dose-proportional. Terminal elimination half-lives were relatively long (25-33 hours in rats and 64-72 hours in monkeys), leading to accumulation in repeat-dose studies (2- to 4-fold increases in rats and 10- to 15-fold increases in monkeys). In the large majority of studies, no differences were observed between males and females (although there were higher exposures in females at the end of the 28-day Good Laboratory Practice [GLP] rat toxicity study). VT-1598 has very high plasma protein binding ( $\geq 99.9\%$ ).

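### The 3-half-life span rule caps the half-life that can be reported, so slower eliminators can lose t1/2, AUC0-inf, CL/F and Vd/F, and reported half-life can be too short

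*SAP*

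**What the plan says.** SAP 10.2 (Noncompartmental Analysis) sets three acceptance criteria for lambda-z: adjusted R-squared of at least 0.90, "Span \geq 3$ half-lives", and at least three points after Tmax. The points are first picked by the WinNonlin algorithm. "Manually chosen timepoints may be used at the discretion of the PK analyst", but a manual set must meet the same criteria. The consequence of failure is broad: "Otherwise, the elimination rate constant and all derived parameters" (t1/2, AUC0-inf, CL/F and Vd/F) become missing for that subject.

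Two other rules in the same section bear on this.

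- If too few subjects pass, "then relaxed Lambda Z Acceptance Criteria may be used and will be described in the CSR". Neither the number that counts as too few nor the content of the relaxed rule is given.
- If more than 20% of AUC0-inf is extrapolated, the value "will be excluded from statistical summaries of PK parameter estimates and downstream calculations". CL/F and Vd/F are treated in the same way.

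The late plasma samples are at 24, 36, 48, 60, 72, 144, 312 and 480 h (Protocol Table 2), the last with a window of ±48 h (Protocol 6.5.1). SAP 10.1 treats values below quantification that follow the first measurable one as missing. The Protocol background (2.1, Pharmacokinetics) gives terminal half-lives of 25-33 h in rats and "64-72 hours in monkeys". It gives none in humans.

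**The concern.** The span criterion divides the length of the regression window by the half-life being estimated. On a fixed sampling schedule it is therefore an upper limit on half-life. Subjects above the limit are removed because their half-life is long, so the loss is informative.

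Reported t1/2 is the parameter most directly exposed. AUC0-inf and CL/F are exposed to the extent that differences in clearance drive differences in half-life, and Vd/F to the extent that volume does. AUC0-inf also feeds the dose-proportionality assessment (SAP 10.3.1) and the fed/fasted ratio (SAP 10.3.3). SAP 15 reports that only one subject returned from Cohort 3 for Cohort 6. The fed/fasted comparison is therefore almost wholly between subjects, and uneven exclusion in the two groups would enter it directly.

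**Working it through.** The plan states no maximum admissible half-life, so there is no figure to reproduce.

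**1. Ceiling implied by the span rule.** Longest half-life that can pass = (last time − first time) / 3, with at least three points in the window. Protocol 9.3 presumes Cmax at 6 h, so the earliest usable point is taken as 8 h.

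| Last quantifiable sample | First point used | Ceiling on t1/2 |
|---|---|---|
| 480 h | 144 h | (480−144)/3 = 112 h |
| 480 h | 72 h | (480−72)/3 = 136 h |
| 480 h | 24 h | (480−24)/3 = 152 h |
| 480 h | 8 h | (480−8)/3 = 157 h |
| 312 h | 72 h | (312−72)/3 = 80 h |
| 144 h | 8 h | (144−8)/3 = 45 h |

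The visit window moves the 157 h figure to between (432−8)/3 = 141 h and (528−8)/3 = 173 h.

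**2. Animal values against the ceiling.** The monkey half-life needs a span of 3 × 64 = 192 h to 3 × 72 = 216 h. The last three samples alone span 480 − 144 = 336 h, so it passes if 480 h is quantifiable. It cannot pass if 144 h is the last quantifiable sample (ceiling 45 h).

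**3. Ceiling implied by the 20% rule.** For a mono-exponential profile the extrapolated share is 2^(−t_last / t1/2). Setting this to 0.20 gives t1/2 = t_last / log2(5): 480/2.32 = 207 h, 312/2.32 = 134 h and 144/2.32 = 62 h. At the span ceilings of 112 h and 157 h, the extrapolated share from 480 h is 5.1% and 12.1%. Subjects between the span ceiling and 207 h therefore lose an AUC0-inf of which only about 5-20% is extrapolated.

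**4. Effect on reported half-life.** Assume lognormal half-lives with geometric mean m, σ² = ln(1 + CV²), and values above the ceiling L set to missing. With z = ln(L/m)/σ, the share kept is Φ(z), and the retained geometric mean relative to the truth is exp(−σ φ(z)/Φ(z)).

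Example: L = 136 h, m = 100 h, CV 30%. Then σ = 0.294, z = 0.307/0.294 = 1.05, share kept 0.853, and ratio exp(−0.294 × 0.231/0.853) = 0.924, so t1/2 is 8% low.

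Each cell below gives results at 30% / 40% CV. Both m and CV are assumptions.

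| Window (ceiling) | m = 72 h: kept; t1/2 low by | m = 100 h: kept; t1/2 low by |
|---|---|---|
| 24-480 h (152 h) | 99.5% / 97%; under 1% / 2% | 92% / 86%; 4-5% / 9% |
| 72-480 h (136 h) | 98.5% / 95%; 1% / 4% | 85% / 79%; 8% / 13% |
| 144-480 h (112 h) | 93% / 87%; 4% / 9% | 65% / 62%; 15% / 21% |
| 72-312 h (80 h) | 64% / 61%; 16% / 22% | not shown |

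**5. Which parameters move.** In a simulation at an assumed median of 150 h, log-scale SD of half-life 0.385 (about 40% CV) and a ceiling of 152 h, the retained geometric means relative to the truth are:

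| Source of variation | t1/2 | AUC0-inf | CL/F | Vd/F |
|---|---|---|---|---|
| Clearance only | 0.74 | 0.74 | 1.35 | 1.00 |
| Volume only | 0.74 | 1.00 | 1.00 | 0.74 |
| Both equally | 0.74 | 0.86 | 1.16 | 0.86 |

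**6. Whether the fallback would act.** If each subject passes with probability 0.65 (the 112 h ceiling at m = 100 h, CV 30%), the binomial chance that 3, 4 or 5 of 6 active subjects pass is 0.81. Those are partial losses, selected by half-life, which an undefined test of too few subjects need not catch.

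**The case against.** The strongest reply is that no loss has been shown. This is a first-in-human study with no human half-life, and the only stated values pass comfortably on a 480 h profile. That stands. A reader might infer that the reported parameters are biased; the documents support only that they can be.

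Other tempting inferences also go too far.

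- **A human half-life near 100 h is implied.** The 10-15-fold monkey accumulation can be turned into a half-life of about 79-121 h if dosing was 12-hourly. The accumulation statement gives no dosing interval, and the Protocol's toxicology text says the accumulation was as expected from 64-72 h. The 100 h case is a scenario, not an estimate.
- **All four derived parameters are biased.** Step 5 shows that this depends on what drives half-life.
- **The span and 20% rules contradict each other.** They do not. One guards the slope and the other the extrapolated share, and both can be applied together. The span rule is simply the stricter one for AUC0-inf.
- **Failures will cluster at the low doses.** No quantification limit or expected human concentration is given, so this cannot be established.

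There are also mitigations. The interim PK analysis may lead to changed sampling times (Protocol 10.4). Listing 30 marks the points used for lambda-z, and the detailed parameter tables show N, so some attrition would be visible. Cmax and AUC0-last are untouched, and the fed/fasted comparison is declared exploratory. These reduce the consequence. They do not remove the dependence of exclusion on half-life, nor define the fallback.

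**Conclusion.** The concern holds in conditional form. By arithmetic on the plan's own schedule, the span rule excludes any subject with a half-life above about 112-157 h when 480 h is quantifiable, above 80 h for a 72-312 h window, and above about 45 h when 144 h is the last quantifiable sample. If some subjects exceed the ceiling, retained t1/2 is biased low, and the other parameters follow according to whether clearance or volume varies.

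The size rests on an assumed half-life, an assumed CV and a lognormal distribution. At 72 h with the 480 h sample quantifiable and a 24 h or 72 h start, it is negligible to small (at most 4% low). At 100 h it is about 4-13% low for those two windows, and more if only the last three samples are log-linear.

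The comparison with the 20% rule needs no human half-life, only the mono-exponential approximation: the span rule discards AUC0-inf values that the extrapolation rule would keep. The fallback is undefined and need not operate when only some subjects fail. This is worth correcting, but it is not evidence that the results are wrong.

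**What to change.** In SAP 10.2:

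- Do not set AUC0-inf and CL/F to missing for span alone when adjusted R-squared is at least 0.90, at least three points after Tmax are used, and %AUCex is at most 20%. The uncertain slope then affects at most a fifth of the AUC.
- For the same subjects, report lambda-z, t1/2 and Vd/F, which depend directly on the slope, flagged as having a span below 3 half-lives. Summarise with and without flagged subjects, for all dose groups and both analytes.
- Keep the relaxed-criteria fallback as a safeguard, but state its trigger and its content in advance.
- Report the number of subjects failing each criterion by dose group.
- Add span and %AUCex to Listings 32 and 33. Protocol 10.6 names %AUCex as a PK parameter, but neither quantity appears there now.

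Simply lowering the threshold to 2 half-lives is not recommended. It would still condition on half-life and only move the ceiling, for example to (480−144)/2 = 168 h for the last three samples.

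The cost is SAP wording, one set of sensitivity summaries, a count by dose group and two listing columns. The downside is that flagged individual lambda-z estimates are less precise, which is why they are flagged and summarised both ways.

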## 10.6 Pharmacokinetic Analysis Plan

Plasma and urine samples from all subjects who received at least one dose of VT-1598 will be analyzed for the concentration of VT-1598 and VT-11134 by validated LC-MS/MS methods. Plasma concentration-time profiles and plots of amount excreted ( $Ae_{(t_1-t_2)}$ ) per urine collection period will be constructed for each subject and each dosing cohort.

The following PK parameters will be estimated, by noncompartmental analysis methods using version 7.0 or higher of Phoenix WinNonlin®, for VT-1598 and VT-11134 plasma and urine concentration, as appropriate.

$C_{\max}$	maximum measured plasma concentration
$T_{\max}$	time to reach maximum measured plasma concentration
$AUC_{\text{last}}$	area under the plasma concentration versus time curve from time 0 to the time of the last quantifiable concentration

---

$AUC_{inf}$	area under the plasma concentration versus time curve from time 0 and extrapolated to infinity
$\%AUC_{ex}$	percentage of $AUC_{inf}$ obtained by extrapolation
$t_{1/2}$	terminal phase half-life
$\lambda_z$	apparent first-order terminal elimination rate constant
$V_d/F$	apparent volume of distribution
$CL/F$	apparent oral clearance
$Ae_{last}$	cumulative amount excreted into the urine from time 0 to the time of the last quantifiable concentration
$Ae_{\%Dose}$	cumulative amount excreted into the urine
$CL_R$	renal clearance of drug

Additional PK parameters may be estimated as appropriate. Dose proportionality for each PK exposure parameter ( $C_{max}$ ,  $AUC_{last}$ ,  $AUC_{inf}$ ) will be assessed statistically and graphically.

The more detailed PK analysis will be available in the SAP for this study.

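### SAP 10.2 divides urine recovery up to the last measurable interval by plasma AUC over the whole 72 h collection, so renal clearance is biased low for subjects whose late urine is BQL

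*SAP*

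**What the plan says.** SAP 10.2 defines the numerator, Ae_last, as the "cumulative amount of drug or metabolite excreted into urine up to the collection time of the last measurable concentration". Protocol 10.6 has the same end point: "cumulative amount excreted into the urine from time 0 to the time of the last quantifiable concentration". SAP 10.2 then sets CL_R equal to Ae_last divided by AUC_0-t1, with t1 "based on the last collected concentration in urine (0 h to 72 h post dose"). CL_R is set to missing only when AUC_0-t1 or Ae_last cannot be estimated.

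SAP 10.1 governs BQL values in both plasma and urine. Those "observed after the first measurable concentration will be treated as missing", and "There will be no imputation of missing concentrations".

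In the SAP table shells, CL_R sits under a 0-72 h inpatient heading for VT-1598 (Tables 87 and 88) and for VT-11134 (Tables 94 and 95). Protocol 10.6 lists CL_R without a formula.

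**The concern.** The numerator ends at the last *measurable* urine and the denominator at the last *collected* urine. The two end times agree only if the 60-72 h sample is measurable. If it is not, the SAP 10.1 rule means that late urine adds nothing to Ae_last, while plasma AUC keeps accruing to 72 h. The missing-value rule does not catch this, because both quantities can still be estimated. A subject with BQL urine after 24 h would get a CL_R built from 24 h of recovery and 72 h of exposure.

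It is tempting to dismiss the lost amount as negligible because it was too small to measure. What matters is its size relative to the amount recovered. With a long half-life, excretion continues at a similar rate after the urine concentration slips under the LLOQ.

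At stake is a planned PK parameter, tabulated for both analytes in every active Dose Group. Subjects within one group could be summarised over different effective windows without any sign of it in the table.

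**Working it through.** The plan states no value for CL_R, so there is no figure to reproduce. The check is the ratio of reported to true CL_R.

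**Inputs**
- Urine intervals end at 6, 12, 24, 36, 48, 60 and 72 h (Protocol Table 3 and Appendix A).
- Plasma is sampled at each of those times (Protocol Table 2). AUC uses linear-up log-down (SAP 10.2).
- Half-life: 25-33 h in rats and 64-72 h in monkeys (Protocol 2.1). Using these for humans is an assumption.
- Tmax: 6 h, the presumed time of Cmax in Protocol 9.3. This is also an assumption; 4 h was tried as a sensitivity check.
- A one-compartment oral profile with constant renal clearance (assumption).

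**Formula.** With constant renal clearance, Ae(0-t) = CL_R × AUC(0-t). Let T be the end of the last measurable urine interval. The SAP's quantity is

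reported CL_R = Ae(0-T) / AUC(0-72) = true CL_R × AUC(0-T) / AUC(0-72),

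so reported/true = AUC(0-T) / AUC(0-72). This is below 1 whenever plasma drug persists after T.

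**Results, Tmax 6 h**

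| Half-life (h) | T = 24 h | T = 36 h | T = 48 h | T = 60 h | T = 72 h |
|---|---|---|---|---|---|
| 25 | 0.533 | 0.712 | 0.841 | 0.934 | 1.000 |
| 33 | 0.483 | 0.664 | 0.805 | 0.915 | 1.000 |
| 64 | 0.405 | 0.584 | 0.741 | 0.879 | 1.000 |
| 72 | 0.396 | 0.574 | 0.733 | 0.874 | 1.000 |

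A Tmax of 4 h moves these ratios by less than 0.02. Outside the animal range, a half-life of 12 h gives 0.715 at T = 24 h and 0.981 at T = 60 h. The limit of flat plasma gives 24/72 = 0.333 and 60/72 = 0.833.

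**Example.** True CL_R 0.100 mL/min, half-life 64 h, urine last measurable at 24 h. The SAP wording gives 0.100 × 0.405 = 0.041 mL/min. With AUC cut at 24 h the result is 0.100 mL/min. Matching the end times gives a ratio of 1.000 at every T, provided that no earlier interval is lost.

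**Intermediate gaps.** Suppose that, at a half-life of 64 h, only the 24-36 h urine is BQL and the 60-72 h urine is measurable. Both windows then end at 72 h, but the numerator lacks 0.584 − 0.405 = 0.179 of the total, and reported/true is 1 − 0.179 = 0.82. Matching end times does not repair this.

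**The case against.** **The text can be read so that the windows match.** The SAP defines a variable t1 rather than fixing 72 h. A late BQL sample is treated as missing, so the last collected concentration could mean the last usable one, with 0-72 h naming only the collection range. The 0-72 h table heading does not settle it, since it also covers Ae_last, which can end sooner. This reading is possible, but it strains the change from measurable to collected within one subsection and the 72 h gloss attached to t1. If it was intended, the SAP still has to say so, because two programmers could derive different CL_R values from this text.

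**The trigger is not established.** The bias needs urine that is measurable early and BQL late. Protocol 2.1 says that "VT-1598 has very high plasma protein binding" (at least 99.9%), and a reader might infer that late BQL urine is therefore likely for both analytes. The documents do not support that: the binding figure is for VT-1598 only, and there is no urine LLOQ and no human urine data. If urine is BQL throughout, there is no last measurable concentration and CL_R should be missing.

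**The largest bias needs a narrow margin.** With half-lives of 64 and 72 h, the modelled 12-24 h excretion exceeds the 24-36 h excretion by a factor of only (0.405 − 0.202)/(0.584 − 0.405) = 1.13 and (0.396 − 0.197)/(0.574 − 0.396) = 1.12. At constant urine flow, the case near 0.40 requires 12-24 h urine barely above the LLOQ. Varying urine volume widens that margin, but it can also make a later interval measurable again. This stands as a reason not to treat the 24 h figures as the expected size.

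**The consequence is limited.** CL_R is not used in the dose-proportionality analysis (SAP 10.3.1) or the food-effect analyses (SAP 10.3.2 and 10.3.3). Listings 30, 31 and 35 would let a reader recompute it. This stands too.

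**Conclusion.** The point holds as a conditional bias in a stated rule. Read literally, SAP 10.2 understates CL_R for any subject whose urine is measurable early but BQL at the end of collection. The understatement is about 7 to 13% if only the last interval is lost, and about 47 to 60% if nothing is measurable after 24 h. Both ranges rest on animal half-lives, a presumed Tmax and a one-compartment profile. The direction needs only that plasma drug persists after the last measurable urine. If the 60-72 h urine is measurable and no earlier interval is lost, there is no bias.

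Two stronger conclusions go too far. A reader might infer that CL_R will rise spuriously with dose, because low doses fall below the LLOQ first. That could happen across 40 to 640 mg, but it depends on an LLOQ that is not given, and no dose analysis of CL_R is planned. A reader might also infer that the trial's main conclusions are affected. They are not: CL_R is a descriptive secondary PK parameter, and the safety, dose-proportionality and food-effect analyses do not use it. The change is worth making because the rule gives a wrong value where late urine is BQL and is cheap to correct.

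**What to change.** In SAP 10.2, define t1 for each subject and analyte as the end of the last urine interval with a measurable concentration, the same end time as Ae_last, and compute AUC_0-t1 to that time. Flag in the CL_R listings and summaries any subject with an intermediate BQL or missing urine interval, since the common end time alone does not remove the bias for them. Amend the 0-72 h heading over CL_R in Tables 87, 88, 94 and 95, or footnote that the window may end earlier.

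The cost is a sentence or two in the SAP, a partial AUC per subject and analyte, and a flag. No new data are needed, because the nominal plasma schedule has a sample at the end of every urine interval.
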